6.3.2. Myometry Parameters

Myometry parameters (knee extension and elbow flexion) will be analyzed using the ANCOVA after MI as described for the primary endpoint and summarized by treatment groups at each visit based on ITT population.

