6.3.2. Myometry Parameters

The myometry parameters will be analyzed using the similar ANCOVA after MI model as 6MWD during overall treatment period for ITT population. The change from study baseline in myometer parameters (knee extension and elbow flexion) will be summarized at each visit during overall treatment period for ITT population.

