6.1.3. Supportive/Sensitivity Analyses

6.1.3.1. Analysis of Covariance (ANCOVA) Using Multiple Imputation (MI)

As a sensitivity analysis, an ANCOVA model will be used to evaluate the difference in change in 6MWD from baseline to Week 72 after missing data have been imputed via a pattern mixture model utilizing MI. The estimated treatment difference in change from baseline of 6MWD at Week 72 and the corresponding 95% confidence interval (CI) will be provided. The ANCOVA model will include baseline concomitant corticosteroid type (deflazacort, prednisone/prednisolone), baseline 6WMD category (<300 meters, 300 to <350 meters, 350 to <400 meters, ≥ 400 meters), treatment, as well as baseline 6MWD as a covariate. For this analysis, all 6MWD will be assigned to an analysis visit according to the analysis visit window described in Section 4.8. Any subjects who lose ambulation during the study will be assigned a 6MWT result of 0 meters for the visit in which the subjects lose ambulation and for all remaining visits while they participate in the study. For subjects with missing 6MWD due to other reasons, the missing assessments at post-baseline visits will be imputed using the pattern-mixture model MI assuming the missing values are missing not at random (MNAR) utilizing the complete case missing value pattern (CCMV - subjects who completed primary efficacy assessments without missing values). Detailed imputation method is described in [Appendix 2](#).

The example SAS code is listed below:

```
PROC MIXED data=<dataset> method=reml;  
  CLASS Cortico Trt C6MWD;  
  MODEL CHG6MWD = Cortico C6MWD Trt B6MWD /CL;  
  LSMEANS TRT / pdiff CL;  
RUN;
```

where

CHG6MWD = change from baseline in 6MWD at Week 72
B6MWD = Baseline 6MWD
C6MWD = Baseline 6MWD category
Cortico = Baseline concomitant corticosteroid type
Trt = Treatment group

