6.1.3.2. ITT and PP Populations

As a supportive analysis, the primary MMRM analysis will be repeated using both the ITT and PP populations. In addition, the ANCOVA model after MI will also be repeated for ITT population. The baseline time to stand from supine (<5 seconds, ≥ 5 seconds) will be included in the testing model in the ITT analysis.

6.1.3.3. *Modification of mITT Criteria (+/- 15%)*

As supportive analyses, separate MMRM models similar to the primary analysis will be used to evaluate the change in 6MWD from baseline to Week 72 for all subjects with a baseline 6MWD ≥ 255 meters (ie, -15% from the 6MWD ≥ 300 meter lower bound) or baseline 6MWD ≥ 345 meters (ie, +15% from the 6MWD ≥ 300 meter lower bound)) and who also meet the age and stand from supine criteria for the mITT population (ie, 7 to 16 years old and time to stand from supine ≥ 5 seconds at baseline).

6.1.3.4. *Checking Missing at Random Assumption*

For the primary analysis, an additional sensitivity analysis will be employed to check the MAR assumption underlying the MMRM model where the reason for drop-out is considered. Subjects with following discontinuation reasons will be imputed using MI method using subjects in placebo arm who completed double-blind period of the study without missing values.

- Adverse event
- Withdrew consent
- Investigator decision

This analysis will be performed for mITT population. Detailed method and SAS codes are described in [Appendix 3](#).

6.1.3.5. *Using Average of Day 1 and Day 2 6MWDs Rather than Maximum*

The primary analysis uses the maximum of valid Day 1 and Day 2 6MWDs for baseline and Week 72. As a sensitivity analysis, the same analysis will be repeated with the average of valid Day 1 and Day 2 6MWDs for baseline and Week 72 for mITT population. For this analysis, the actual week for Baseline and Visit 8 will be calculated based on the first day of the visit.

6.1.3.6. *Assess the Impact of COVID19*

To assess the impact of COVID19, a sensitivity analysis will be performed similarly to the primary MMRM analysis and ANCOVA analysis after MI by removing all COVID19 impacted visits (as collected on CRF) for mITT and ITT populations. The baseline time to stand from supine (<5 seconds, ≥ 5 seconds) will be included in the testing model in the ITT analysis.

6.1.3.7. *Assess the Impact from Potential Correlation among Siblings*

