6.2.1.2. North Star Ambulatory Assessment - Total Scores

The NSAA consists of 17 activities, each scored as 0, 1, or 2. The sum of 16 scores (except for lifts head) will be used to form a total score [Mayhew 2013a]. Hereafter, this NSAA total score will be referred to as revised NSAA (rNSAA) total score. If an activity cannot be performed due to disease progression/LoA, a score of 0 will be assigned, and will not be considered as missing. If fewer than 13 of the 16 activities are performed, the total score will be considered missing. If from 13 to 16 activities are performed, the total score will be standardized by multiplying the sum of the scores in the x activities by 16/x.

The change from baseline in rNSAA total score at Week 72 based on the mITT population will be the second key secondary endpoint. An ANCOVA model will be used to evaluate the difference in change in rNSAA from baseline to Week 72 after missing data have been imputed via a pattern mixture model utilizing MI. The ANCOVA model will include factors of baseline

concomitant corticosteroid type (deflazacort, prednisone/prednisolone), baseline 6WMD category (<300 meters, 300 to <350 meters, 350 to <400 meters, \geq 400 meters), and treatment, and covariate of baseline rNSAA total score. The estimated difference in the change at Week 72 will be provided.

If both primary efficacy endpoint and the first key secondary endpoint are statistically significant at the 0.05 significance level, the rNSAA will be tested at the 0.05 (two-sided) significance level.

The same ANCOVA model will also be performed on linear transformation of the total score [Mayhew 2013a].

As a sensitivity analysis, rNSAA total score and linear score will be analyzed using a MMRM model with a random intercept. The MMRM model will include baseline concomitant corticosteroid type (deflazacort, prednisone/prednisolone), baseline 6WMD category (<300 meters, 300 to <350 meters, 350 to <400 meters, \geq 400 meters), treatment, visit (analysis visit as a categorical variable), the baseline rNSAA score as the covariate, as well as interaction of visit and treatment, and the interaction of visit and baseline rNSAA total score. The unstructured covariance matrix (UN) will be used in the MMRM model. Other types of covariance matrix (heterogenous Toeplitz, Toeplitz, and compound symmetric) will be explored in the case of non-convergence of UN.

A sample code is listed as below:

```
PROC MIXED data=<dataset> method=reml;  

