6.3. Exploratory Variables

6.3.1. PUL and DMD Upper Limb PROM

PUL includes 22 items (with an entry item to define starting functional level), and 21 items subdivided into shoulder level (4 items), elbow level (9 items), and distal level (8 items) dimensions. The DMD Upper Limb PROM includes 32 items categorized in 4 domains of daily life: food (7 items), self-care (8 items), household and environment (6 items), and leisure and communication (11 items). The domain subscores will be calculated by summing the scores from all items within each domain, and the total score will be calculated as the sum of all domain scores. A domain subscore is considered missing if any of the individual item is missing within the respective domain. The total score is considered missing if any of the individual item is missing from a giving assessment.

The PUL and DMD Upper Limb PROM total scores will be summarized and analyzed separately using the ANCOVA after MI based on both mITT and ITT populations. The ANCOVA model will include baseline concomitant corticosteroid type (deflazacort, prednisone/prednisolone), baseline 6WMD category (<300 meters, 300 to <350 meters, 350 to <400 meters, ≥400 meters), and treatment as factors, and respective baseline scores as a covariate. The baseline time to stand from supine (<5 seconds, ≥5 seconds) will be included in the testing model in the ITT analysis.

The frequency of losing each PROM item will also be tabulated by treatment group for mITT and ITT populations.

In addition, the PUL total and domain subscores will also be summarized by age group (7 to <8 years old, 8 to <13 years old, 13 to <22 years old, and ≥ 22 years old) using descriptive statistics within each treatment group for mITT and ITT populations. The last assessment during the specific age group will be used for a given subject in this summary.

The PUL total and domain subscores will also be summarized and analyzed for subjects with the following subgroups for ITT population:

- Baseline 6MWD <300 meters
- Baseline 6MWD ≥ 300 meters and time to rise from supine <5 seconds at baseline, or baseline 6MWD ≥ 300 meters, time to rise from supine ≥ 5 seconds at baseline, and younger than 7 or older than 16 years old

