proc sort data=smwt_mono out=smwt_mono; by _imputation_ trtn usubjid; run;
proc MI data=smwt_mono out=smwt_ccmv minimum=0 nimpute=1 minmaxiter=5000
seed=93035;
  WHERE mITTfl="Y";
  BY _imputation_ trtn;
  VAR SmwdWKBL SmwdWK12 SmwdWK24 SmwdWK36 SmwdWK48 SmwdWK60 SmwdWK72;
  MONOTONE reg(/details);
  MNAR Model (SmwdWK12 SmwdWK24 SmwdWK36 SmwdWK48 SmwdWK60
SmwdWK72/Modelobs=CCMV);
run;
```

* 3rd: Create datasets for ANCOVA;

```
data smwt_reg;
  set smwt_ccmv;
  AWeek= 0; Avalimp=SmwdWK0; CFBimp=SmwdWK0-BL6mwd; output;
  AWeek=12; Avalimp=SmwdWK12; CFBimp=SmwdWK12-BL6mwd; output;
  AWeek=24; Avalimp=SmwdWK24; CFBimp=SmwdWK24-BL6mwd; output;
  AWeek=36; Avalimp=SmwdWK36; CFBimp=SmwdWK36-BL6mwd; output;
  AWeek=48; Avalimp=SmwdWK48; CFBimp=SmwdWK48-BL6mwd; output;
  AWeek=60; Avalimp=SmwdWK60; CFBimp=SmwdWK60-BL6mwd; output;
  AWeek=72; Avalimp=SmwdWK72; CFBimp=SmwdWK72-BL6mwd; output;
run;
```

...

* 4th: Conduct ANCOVA analysis on imputed datasets;

```
proc sort data=adsmwdimp out=adsmwdimp; by _imputation_; run;
ods exclude all;
proc mixed data=adsmwdimp method=REML;
  WHERE mITTfl="Y" and Aweek=72;
  BY _imputation_;
  CLASS Cortico Trtn C6mwd;
  MODEL CFBimp=BL6MWD Trtn Cortico C6MWD / CL;
  LSMEANS Trtn/ diff=control('0') cl alpha=0.05;
  ods output diffs=diff_mi lsmeans=lsn_mi;
run;
ods exclude none;
```

* 5th: Use Proc MIAnalyze to obtain final analyiss results;

* LS Means;

```
proc mianalyze parms(classvar=full)=lsn_mi;
  CLASS Trtn;
  MODELEFFECTS Trtn;
  ods output parameterestimates=lsn_out;
run;
```

* Treatment differences;

```
proc mianalyze parms(classvar=full)=diff_mi;
  CLASS Trtn;
  MODELEFFECTS Trtn;
  ods output parameterestimates=diff_out;
run;
```

The table below lists the random seeds to be used for the primary and secondary analyses and some additional seeds should they be required. The random seeds were created using SAS uniform generator RAND("Uniform") with a seed of 20210126.

| Endpoint/Analysis | Seed for Step 1 (impute missing interim data) | seed for Step 2 (impute missing ending data) |
|--|---|--|
| 6MWD (mITT, Section 6.1.2) | 93182 | 93035 |
| 6MWD (ITT, Section 6.1.3.2) | 31096 | 27324 |
| 6MWD (PP, Section 6.1.3.2) | 96919 | 60747 |
| 6MWD (Covid19 impact, mITT, Section 6.1.3.6) | 57237 | 96213 |
| 6MWD (Covid19 impact, ITT, Section 6.1.3.6) | 81564 | 23187 |
| NSAA (mITT, Section 6.2.1.2) | 53056 | 44931 |
| NSAA (ITT, Section 6.2.1.2) | 78128 | 55295 |

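### Neither SAP names the baseline covariate for myometry; read literally, strength change is adjusted for baseline walking distance and not for baseline strength

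*SAP*

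**What the plan says.** Double-blind SAP 6.3.2 gives the myometry model only by reference: it "will be analyzed using the ANCOVA after MI as described for the primary endpoint". That model is set out in 6.1.3.1, with corticosteroid type, baseline 6MWD category, "treatment, as well as baseline 6MWD as a covariate". Appendix 2 codes it as "MODEL CFBimp=BL6MWD Trtn Cortico C6MWD / CL". For ITT, the population used for myometry, 6.1.3.2 adds the stand-from-supine factor, which "will be included in the testing model in the ITT analysis". None of these terms measures strength.

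Other endpoints in the same SAP have their own baseline spelled out. The rNSAA ANCOVA (6.2.1.2) has the strata "and treatment, and covariate of baseline rNSAA total score". The PUL and PROM ANCOVA (6.3.1), directly before myometry, has the strata "and treatment as factors, and respective baseline scores as a covariate". The MMRMs for the timed function composite (6.2.1.1) and the individual tests (6.2.2.2) also list their own baseline.

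Section 4.3 provides for baseline covariates for primary and secondary endpoints; myometry is listed as exploratory (2.3.3). Baseline myometry is measured at Visit 2 (2.7.4).

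The open-label SAP (6.3.2) reads: "The myometry parameters will be analyzed using the similar ANCOVA after MI model as 6MWD". The later document on changes from the planned analysis (3.3.2) leaves myometry as it was.

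**The concern.** A change score that is not adjusted for its own baseline usually carries variance that baseline adjustment would remove. Any chance difference between arms in starting strength then feeds into the comparison through regression to the mean. Baseline walking distance can stand in for starting strength only as far as the two are correlated.

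Myometry is done only in boys under 7. Randomisation was stratified by corticosteroid type, 6MWD and stand time, not by age or strength. These boys are also outside the mITT population, and the protocol (11.1.5) expects a strength effect to show more clearly in younger patients. What is at stake is the precision of an exploratory comparison, and whether two programmers working from the same text would fit the same model.

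**Working it through.** **Plan's own figure.** There is none for myometry: no N, SD, correlation or power. The only sample size is for the 6MWD slope (double-blind SAP 2.4). It reproduces: 2 × 2.058² × (1.960 + 1.036)² / 1.0² = 76.03, so 77 per arm and 154 in total, with power 85.4%. It does not bear on this point.

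**Set-up.** The outcome is D = Y − B, Week 72 strength minus baseline strength, with baseline SD set to 1. None of these inputs is in the documents, so ranges are assumed:
- ρ, correlation of baseline and Week 72 strength: 0.5 to 0.9
- k, SD at Week 72 divided by SD at baseline: 1, then 1.25
- r, correlation of baseline 6MWD (W) and baseline strength: 0 to 0.5

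W is taken to predict Week 72 strength only through baseline strength.

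**Residual variances.**
- Literal model: Var(D|W) = 1 + k² − 2ρk − r²(ρk − 1)²
- Own baseline: Var(D|B) = k²(1 − ρ²)
- Gap: (1 − r²)(1 − ρk)², which is never negative and is zero when ρk = 1

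**Equal SDs (k = 1).**

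| ρ | Var(D\|W), r = 0 to 0.5 | Var(D\|B) | SE ratio, literal / own baseline | Equivalent share of boys lost |
|---|---|---|---|---|
| 0.5 | 1.000 to 0.938 | 0.750 | 1.155 to 1.118 | 25% to 20% |
| 0.7 | 0.600 to 0.578 | 0.510 | 1.085 to 1.064 | 15% to 12% |
| 0.9 | 0.200 to 0.197 | 0.190 | 1.026 to 1.020 | 5% to 4% |

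The SE ratio is √(Var(D|W)/Var(D|B)), and the last column is 1 − Var(D|B)/Var(D|W). For ρ = 0.5 and r = 0, √(1.000/0.750) = 1.155 and 1 − 0.750 = 25%.

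**SD growing by a quarter (k = 1.25).** The SE ratio is 1.058 to 1.044 at ρ = 0.5, about 1.01 at 0.7 and 1.026 to 1.020 at 0.9. At ρ = 0.8 both variances are 0.5625 and nothing is lost, because 0.8 × 1.25 = 1.

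**Simulation check.** The full ANCOVA with corticosteroid, 6MWD-category and stand-time factors was simulated with equal SDs and an assumed 30 boys per arm. The SE ratios were 1.12-1.15, 1.06-1.08 and 1.02-1.03 at ρ = 0.5, 0.7 and 0.9, which agrees with the formulas.

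**Chance imbalance.** With r = 0, a baseline difference of d between arms shifts the change-score comparison by (ρk − 1)d. For k = 1 and ρ = 0.5 that is half of d, in the opposite direction. Adjustment for own baseline removes it.

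**The case against.** The strongest reply is that the 6MWD model is a template and that own baseline is implied. In Appendix 2 the variable subtracted to form the change score is also the covariate, so replacing baseline 6MWD by baseline strength throughout would supply the missing term. In the 6MWD model, baseline 6MWD is itself the endpoint's own baseline. The rNSAA sample code keeps 6MWD variable names although the text asks for baseline rNSAA. The composite timed-function section calls its model the same as the primary one and then lists its own baseline. The open-label NSAA and PUL/PROM sections use the same shorthand as open-label myometry, and the double-blind ANCOVA for individual timed tests names no covariates at all. Section 4.3 does not exclude baseline covariates for exploratory endpoints.

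This stands as evidence of possible intent, and it rules out saying that the sponsor chose to leave baseline strength out. It does not settle the model. A programmer could replace the subtracted baseline and keep the 6MWD covariate, and nothing in the text would say that was wrong.

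A reader might also infer that the loss is worse because the subset is small. The SE ratio above does not depend on sample size, and the documents do not give the number of boys under 7. Nor is there systematic bias: chance imbalance averages to zero under randomisation.

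**Conclusion.** The point holds as a gap in specification. The covariate is unnamed in both SAPs, and the literal reading gives a comparison that is less precise than, or at best as precise as, one using a baseline already collected. With equal SDs the standard error is about 2-15% larger over the assumed range of ρ from 0.9 down to 0.5. The figure is conditional, because ρ, k and r are all assumptions, and the loss shrinks or vanishes if the spread of strength grows as the boys grow.

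It would be tempting to conclude that the myometry comparison does lose precision, or that the trial's conclusions are weakened. The documents support neither: the analysis may have been run with own baseline, and myometry is exploratory, unpowered and outside the fixed testing sequence (double-blind SAP 4.6). No confirmatory conclusion changes. This is a minor but nearly free improvement.

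**What to change.** In 6.3.2 of both SAPs, state that the myometry ANCOVA uses the baseline value of the same muscle-group measure as covariate, in place of or in addition to baseline 6MWD; that it keeps the stratification factors; and that the imputation model uses that same baseline. Several readings are taken on each side, so say that the baseline is derived in the same way as the post-baseline value.

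For the double-blind period, which the open-label SAP reports as soft-locked on 11 April 2022, record this as a documented clarification and state which model was fitted. The open-label SAP describes the final lock as still to come, so there it can be an ordinary amendment.

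The cost is one sentence per SAP, no new data, and one degree of freedom if baseline strength is added rather than substituted.

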6.3.3. Muscle Fat Fraction

Muscle fat fraction data obtained (proton density fat fraction and MRS fat fraction) from MRI will be summarized by treatment groups at each visit based on both the mITT and ITT populations. The muscle fat fraction will also be summarized for subjects with the following subgroups:

- Baseline 6MWD <300 meters
- Baseline 6MWD ≥ 300 meters and time to rise from supine <5 seconds at baseline, or baseline 6MWD ≥ 300 meters, time to rise from supine ≥ 5 seconds at baseline, and younger than 7 or older than 16 years old

6.3.4. Spirometry - Pulmonary Function Test

The change from baseline in FVC assessments (FVC, FEV1, and PEF) and %-predicted FVC will be summarized in 12-week intervals from the time of LoA visit based on both mITT and ITT populations. The baseline of FVC assessment is defined as the FVC assessment taken at the visit when subjects become non-ambulatory in this analysis.

Predicted FVC will be calculated as [Gauld 2003]:

$$\text{Predicted FVC} = \exp(0.077 * \text{ulna length} + 0.041 * \text{actual age} - 1.285)$$

%-predicted FVC will be calculated as:

$$\text{\%-predicted FVC} = \text{observed FVC} / \text{predicted FVC} * 100\%$$

Other spirometry parameters including maximum inspiratory (MIP) and expiratory pressures (MEP) will be presented in subject listings only.

6.3.5. HRQL At-Home Questionnaires

HRQL data obtained from the EQ-5D and DMDSAT will be summarized by treatment group at each visit based on both mITT and ITT populations.

The EQ-5D questionnaire has two components, health state description and evaluation. The descriptive part consists of health-related quality of life questionnaires covering 5 dimensions (mobility, self-care, usual activities, pain/discomfort, anxiety/depression). Respondents score each dimension, which results in a one-digit number that expresses the level selected (no problems, some problems, extreme problems) for that dimension. In the evaluation part, the respondents evaluate their overall health status using the visual analogue scale (EQ-VAS). The domain scores will be tabulated, and the mean and mean change in EQ-VAS will be summarized by treatment groups at each visit for mITT and ITT populations.

The DMDSAT comprised a total of eight questions covering four domains (arm function, mobility, transfers, and ventilation status). The domain scores will be summed up to form the total scores. The domain scores will be tabulated and the mean and mean change in total score will be summarized by treatment groups at each visit for mITT and ITT populations.

7. SAFETY EVALUATION

Derived analysis visits based on analysis window described in Section 4.8 will be used for safety analysis, unless otherwise specified.

7.1. Adverse Events

AEs will be coded to the MedDRA (Version 24.1 or higher) lower level term closest to the verbatim term. The linked MedDRA PT and primary system organ class (SOC) are also captured in the database. The severity of AEs will be graded using the latest version of the Common Terminology Criteria for Adverse Events (CTCAE), Version 5.0 whenever possible.

For the double-blind treatment period, a treatment-emergent adverse event (TEAE) is defined as an adverse event that:

- Occurs or worsens during the double-blind treatment period (Day 1 to within 4 weeks of last double-blind treatment, and prior to the first open-label treatment) for subjects who complete the double-blind treatment period; and
- Occurs or worsens from the period extending from Day 1 to 4 weeks after the last dose of double-blind study drug for subjects who discontinue from the study early during the double-blind treatment period, or who complete double-blind treatment period but not enroll into open-label treatment period.

Only those AEs that are treatment-emergent will be included in summary tables. All AEs, treatment-emergent or otherwise, will be presented in subject data listings. An overview table of TEAEs, including number of subjects with TEAEs, treatment-emergent serious adverse events (TESAEs), deaths, TEAEs classified as CTCAE Grade 3 or higher, study drug related TEAEs, TEAEs leading to study drug withdrawal will be provided for each treatment group. The following summaries will be produced for the TEAEs by treatment group:

- Incidence of TEAEs by SOC and PT
- Incidence of TEAEs by PT in descending order
- Incidence of treatment-related TEAEs by SOC and PT
- Incidence of TEAEs by SOC, PT, and maximum CTCAE grade
- Incidence of TEAEs by SOC, PT, and relationship to treatment.

In the summary tables subjects may be counted under multiple SOC and PTs, but for each SOC and PT, subjects are only counted once. If a subject has the same AE on multiple occasions, the highest severity (5=fatal, 4=life-threatening, 3=severe, 2=moderate, 1=mild) recorded for the event will be presented and the highest drug relationship (1 = 'Unrelated', 2 = 'Unlikely to be Related', 3 = 'Possibly Related', 4 = 'Probably Related'), reclassified into Related ('Possibly Related', 'Probably Related') or Not Related ('Unrelated', 'Unlikely to be Related'), will be presented on the respective tables.

The following summaries will also be presented for the TESAEs:

- Incidence of TESAEs by SOC and PT
- Incidence of TESAEs by PT in descending order

- Incidence of treatment-related TESAEs by SOC and PT.

In addition, number and percentage of subjects with TEAEs and treatment-related TEAEs leading to discontinuation from study treatment will also be summarized by MedDRA SOC and PT for each treatment group.

SAE, AE leading to discontinuation from study treatment, and death will be listed.

